◆ Retaining of liver puncture specimen: Fix with 10% neutral formalin, retain additionally 6 white films at every unit, and send it to the pathological examination center (the quality control is shown in Appendix 1).

3. Hematological examination: (the quality control is shown in Appendix 1)

(1) Routine blood tests;

(2) PT, PTA, INR;

(3) TP, ALB, AST, ALT, CHE, GGT, ALP, TBA, TBIL, DBIL, GLU, TC, TG, HDL, LDL, BUN, Cr;

(4) AFP;

(5) Serum virological indices: hepatitis B test (five-item), HBV-DNA assay, HCV antibody test, HIV antibody test; HDV antigen test.

4. Ultrasonic examination:

Within three months after the liver biopsy, the ultrasonic examination is made at an empty stomach for ≥ 8 h. The inner diameter of liver, spleen, gallbladder, portal vein and splenoportal vein is measured through the ordinary two-dimensional ultrasonic examination. The echo data of liver surface/edge/parenchyma and gallbladder wall is scored to evaluate the severity of fibrosis. At every center, the operation should be made via the fixed machine by the fixed person, so as to prevent the artificial error; and the ultrasonic examination, the elasticity determination of liver tissues and the collection of medical history should be made in the same day.

Semi-quantitative Scoring Criteria at Liver Ultrasonic Examination

Score Item	1 score	2 scores	3 scores
Liver surface (Ls)	Smooth, flat	Unsmooth, fine water ripple	Wave, saw-shaped or discontinuous
Liver parenchyma (Lp)	Fine spot, uniform distribution	Slightly enhanced, coarse particle of non-uniform	Obviously echo enhanced, particulate or nodular echo group

		distribution	
Gallbladder wall (G)	Smooth	Coarse, slightly thickened	Obviously thickened or two-side sign

5. Liver Stiffness Measurement (LSM)

Within 3 months before and after the liver biopsy, the liver stiffness measurement (LSM) values are determined via FibroTouch.

◆ Investigators will operate the FibroTouch system to measure the patients' values of liver stiffness and fat attenuation parameters according to the SOP of FibroTouch.

<1>. Subjects lie in face-up position, and stretch his or her right arm to the maximum extent or cross behind his or her head. Enter the name, gender, birth date, medical card No., height, weight and other information into patient information log in FibroTouch system.

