<2>. In order to determine accurately, image-guided positioning with ultrasonic B probe should be performed prior to the scanning with liver fibrosis probe. Apply ultrasonic coupling agent to the patient's skin at the position of right side, interspace between the Seventh and eighth rib along the midaxillary line, place the ultrasonic B probe perpendicularly on the skin, and then turn on the FibroTouch image-guided scanning model. Investigator can choose the proper position for liver examination with reference to the ultrasonic B image on the video display screen.

The testing position (at the center line of ultrasonic B image) is selected as following roles:

1. Be away from the heterogeneous liver tissues, such as great vessels, cysts and nodes.
2. Be away from the edge of liver.
3. The position where liver tissue are homogeneous, well-proportioned and with thickness no less than 7cm.

<3>. Save the ultrasonic B image, hang off ultrasonic B probe from the selected position, and change to liver fibrosis scanning model. Hold the fibrosis scanning probe in right hand, bend forefinger to keep probe perpendicularly at the selected position on the skin, lie right elbow on the bed (to avoid the right arm from shaking and moving), and left hand hold the tail of the probe to control the direction. Press the probe slightly on patients' skin to make the pressure indicating strip turn green.

<4>. With subject holding his or her breath slightly, operator observes the liver tissue displayed by ultrasonic-M signal. When the tissue is dark, more homogeneous and laminar distribution, the operators can press down the foot switch, and the fibrosis scanning probe sent out low-frequency shear waves for diagnosing and ultrasonic waves for monitoring, the probe is activated and complete once examination of LSM.

<5>. Ten times of successful detection are performed at the same position. When the inter

quartile range (IQR) value is qualified, the median value of these detections will be considered as the examination result of LSM.

<6>. Save and print the test result.

◆ The operator of FibroTouch must be trained by Hisky and obtain an operating license or certificate.

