◆ A successful and effective test by FibroTouch must meet the following requirements: ultrasonic-A signal does not have intensive and rapid shaking, and does not fluctuate significantly in different depth; ultrasonic-M signal does not have big difference of lightness and displays a laminar distribution pattern in different depth; ultrasonic-E signal presents a routine white-and-black twill diagram.

◆ Each subject will obtain 10 successful acquisitions and the median value of these acquisitions will be considered as the examination result of LSM and FAP. The IQR-to-median ratio of the 10 acquisitions should be ≤ 0.3 (the smaller the IQR value, the reliable the result is). If the result is not reliable, it should be detected again until the result is reliable.

◆ To avoid artificial errors, the instrument needs to be operated by a fixed professional in each site, and all information will be documented in a uniform model and stored in U-disk, keep by a designated personnel.

6. FibroScan Examination

6.1 At the same site as that for FibroTouch, the stiffness of liver is determined via Fibroscan at the same day.

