6.2 Operation procedure

(1) Keep in a supine position, lift up both hands to expose the intercostal gap in the area of right liver lobe of chest, and take a deep breath to make the intercostal gap as large as possible at the time of determination.

(2) Vertically stick the probe smeared with coupling agent to the intercostal gap.

(3) Determination site: Select the intercostal gap at the anterior or middle axillary line between the Rib 8~10 for routine determination, or adjust the determination site until the optimal one according to the real-time audiovisual diagram if the determination fails at the routine site.

(4) Observe the audiovisual diagram displayed in the instrument, and press the emission button for determination when there is a laminar liver image.

(5) Determine effectively for 10 times, and regard the mean of these 10 determinations as the determination result.

7. Liver biopsy

Within 3 months before the FibroTouch examination, puncture the 16G liver biopsy needle into 1.5~2.0cm of liver tissues (≥ 8 complete portal areas), fix with 10% neutral formalin, embed with paraffin wax, make the continuous section for HE, Masson and reticular fiber staining (make the HE staining at every study unit, and send another 6 white films to the central laboratory). Then, three pathologists interpret the films independently according to the standard and modified Chevallier semi-quantitative scoring method in the “Protocol for Prevention and Treatment of Viral Hepatitis (2001)”. The interpretation result of these three pathologists should be verified as well consistent through the Kappa test, and otherwise the specimen of inconsistent interpretation result is sent for central interpretation and evaluation.

(1) The liver fibrosis is staged and scored through the following protocol:

① National Protocol for Prevention and Treatment of Viral Hepatitis (2000): staging of liver fibrosis

② Chevallier System (SSS scoring)

③ Metavir System

④ Ishak System

(2) Evaluation protocol for inflammatory activity level and histological activity index (HAI):

① National Protocol for Prevention and Treatment of Viral Hepatitis (2000): grading of inflammation severity

② Ishak Modified HAI: ____/18 (maximum score)

③ METAVIR System: histological activity score

(IV) Safety Evaluation

1. Clinical Safety Evaluation

The clinical safety is evaluated through the adverse events reported by the patients or observed by the doctors.

2. AE

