◆ By grouping according to the grading result via golden standard, the inter-group comparison is made on the FibroTouch determination results through the variance analysis or Wilcoxon rank-sum test, the correlation between two groups is tested through the Spearman correlation analysis, and the correlation coefficient (r) and 95% CI are calculated for two groups.

◆ By regarding the different grading results of golden standard as the judgment critical point, the curve of receiver operating characteristic (ROC) for elasticity value is constructed. The subjects are grouped by regarding the different determination results of elasticity value as the judgment critical point, the sensitivity/specificity is calculated according to the grading result of golden standard, the ROC curve is plotted through the X-axis of specificity, the Y-axis of sensitivity and the calculated result, and the area under curve and its 95% confidence interval are calculated. The critical value corresponding to whichever is greater for the result of sensitivity and specificity is regarded as the judgment critical point for FibroTouch determination value, and then the corresponding sensitivity, specificity, positive predicted value and negative predicted value are calculated.

Comparison of secondary objective: by statistically assuming the success rate of FibroTouch is non-inferior to that of Fibroscan, the critical value of non-inferiority is 10%; and by statistically assuming the determination result of FibroTouch is equivalent to that of Fibroscan, the critical value of equivalence is 1.5KPa.

In the above analysis, $P < 0.05$ indicates a significant difference.

(VIII) Data Management and Data Traceability

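### FibroTouch, FibroScan and the ultrasound score are taken on one day with no order set and no earlier result withheld, so the secondary comparisons are open to review bias and order effects

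*Combined protocol and SAP*

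**What the plan says.** All places are in the combined protocol and SAP.

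- **Timing.** Section IX (III) item 4 asks that "the ultrasonic examination, the elasticity determination of liver tissues and the collection of medical history should be made in the same day". Item 6.1 adds FibroScan: "At the same site as that for FibroTouch, the stiffness of liver is determined via Fibroscan at the same day".
- **Ultrasound.** Item 4 has the examiner grade liver surface, parenchyma and gallbladder wall from 1 to 3 to judge fibrosis severity. It asks at each centre that "the operation should be made via the fixed machine by the fixed person".
- **FibroTouch.** Item 5 places the probe at the "interspace between the Seventh and eighth rib along the midaxillary line", guided by a B-mode image. Ten successful acquisitions are summarised by their median. The test is repeated if the ratio of IQR to median exceeds 0.3, and the result is saved and printed. One fixed professional per site operates the device.
- **FibroScan.** Item 6.2 has its own location rule: "Select the intercostal gap at the anterior or middle axillary line between the Rib 8~10 for routine determination". If that fails, the operator may "adjust the determination site until the optimal one according to the real-time audiovisual diagram". The operator is to "press the emission button for determination when there is a laminar liver image". Ten determinations are summarised by their mean, and no IQR or repeat rule is given.
- **Use of the data.** Section II (II) lists the FibroTouch and FibroScan success rates, their measured values, and the correlation of FibroTouch with the ultrasound score as secondary objectives. Section IX (VII) sets a 10% non-inferiority margin for success and, for values, "by statistically assuming the determination result of FibroTouch is equivalent to that of Fibroscan, the critical value of equivalence is 1.5KPa".
- **Independent reading.** Item 7 requires it of the three pathologists. Nothing comparable is asked of the people who perform ultrasound, FibroTouch and FibroScan.

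**The concern.** When two tests are compared in the same patient on the same day, two things can contaminate the comparison. The first is review bias: an examiner who knows the earlier result may let it shape the later one. The second is an order effect: anything that differs between a first and a second measurement is counted as a difference between tests unless order is balanced or modelled.

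The plan guards against neither. Its text sets no sequence for the three examinations, does not balance it, does not ask for it to be recorded, and keeps no result from the next examiner. Three secondary comparisons depend on these data, and two of them carry formal margins. An order that was never recorded cannot be adjusted for later, and a reading made with knowledge of another cannot be unmade.

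**Working it through.** The plan gives no figure for an order or masking effect, so there is nothing to reproduce. The check sets the passages side by side and then asks how large an effect would have to be.

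**1. What the text fixes**

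| Feature | Ultrasound score | FibroTouch | FibroScan |
|---|---|---|---|
| Same day | yes (item 4) | yes (item 4) | yes (item 6.1) |
| Place in the sequence | not stated | not stated | not stated |
| Masked to the other results | not stated | not stated | not stated |
| Operator | fixed person | fixed professional | not stated |
| Source of the value | examiner's grade | device, median of 10 | device, mean of 10 |
| Operator's discretion | the grade itself | position, when to fire, repeat if unreliable | when to fire, move site after failure |

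The text does not say whether the ultrasound examiner also runs either device.

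**2. Order effect on the stiffness difference**

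Let Δ be the true mean difference (FibroTouch minus FibroScan), δ a shift added to whichever reading comes second, and p the share of patients scanned with FibroTouch first.

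Observed mean difference = Δ − pδ + (1 − p)δ = Δ + (1 − 2p)δ.

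- p = 1 gives Δ − δ.
- p = 0 gives Δ + δ.
- p = 0.5 gives Δ.

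The plan gives neither p nor δ. A constant shift cancels only if order is balanced, and it can be estimated only if order is recorded.

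**3. Pull of the second stiffness reading toward the first**

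Suppose the second reading moves a fraction f of the gap toward the first. The observed difference is then (1 − f) times the true one, whichever device goes first. The 1.5 kPa margin in effect becomes 1.5/(1 − f): 1.67 kPa at f = 0.1, 1.88 at 0.2 and 2.14 at 0.3.

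For the chance of declaring equivalence, take n = 500 (Section V) and margin 1.5 kPa (Section IX (VII)). These inputs are assumed, not in the documents: two one-sided tests at 5% each, a true difference of 2.0 kPa, and an SD of paired differences of 5 or 8 kPa.

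D = 2.0(1 − f), se = SD(1 − f)/√500, and

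P = Φ[(1.5 − D)/se − 1.645] − Φ[(−1.5 − D)/se + 1.645].

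Example with f = 0.4 and SD 5: D = 1.2, se = 3/22.36 = 0.134, and 0.3/0.134 − 1.645 = 0.59. This gives P = 0.72; the second term is negligible.

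| f | D (kPa) | P, SD 5 | P, SD 8 |
|---|---|---|---|
| 0 | 2.0 | 0.000 | 0.001 |
| 0.10 | 1.8 | 0.001 | 0.005 |
| 0.25 | 1.5 | 0.05 | 0.05 |
| 0.40 | 1.2 | 0.72 | 0.40 |
| 0.50 | 1.0 | 1.00 | 0.88 |

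A 10% pull is harmless here. The error passes 5% only when f exceeds 0.25, the point at which 2.0(1 − f) falls to the margin.

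**4. Ultrasound score**

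The grade is the examiner's judgement of fibrosis severity, and the kPa is a reading on the same question. An examiner who knows it would tend to grade in line with it, which raises the correlation. The documents give no basis for a figure.

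**5. Success rate**

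A position found during one examination could help or hinder the other device, and the order is unknown. Neither size nor direction can be derived.

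**6. Measurement site**

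Item 5 names the interspace between ribs 7 and 8 on the midaxillary line. Item 6.2 names ribs 8 to 10 on the anterior or middle axillary line. Item 6.1 says the site is the same. If site means position on the body, these conflict. If it means centre, as in the sentence just before 6.1, the two devices may measure different places.

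**The case against.** The strongest reply is that same-day pairing is good design, because it removes real change in the liver between the two measurements. That stands; the gap is pairing without control of order or knowledge. Each device also computes its own value from ten acquisitions, and the operator fires on the image, not on the kPa. That stands too, and step 3 shows that a modest pull would do little. For ultrasound, nothing says that the examiner sees the kPa. This is true, but nothing prevents it either.

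Three stronger readings are tempting, and the documents do not support them:

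- *FibroTouch always comes first.* A reader might infer this because 6.1 defines the FibroScan site by reference to FibroTouch. But 6.1 states no sequence, the word site may mean centre, and 6.2 gives FibroScan its own location. The order of the items is no guide: biopsy is listed last, yet item 7 puts it before FibroTouch.
- *Device is fully confounded with order.* This would follow only from a fixed order. The text leaves the order open.
- *The comparisons are biased toward agreement.* A known first result could pull that way. Different rib spaces, median against mean, and a reliability rule for one device only would tend to reduce agreement. An order effect can go either way. The net direction for the device comparison is unknown.

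**Conclusion.** The point holds as a gap in control, not as a demonstrated bias. In the text, order and masking among FibroTouch, FibroScan and ultrasound are unspecified, so review bias and order effects cannot be excluded from the secondary comparisons. The flow chart in Appendix 2 was not available to this review and should be checked for a sequence; a sequence alone would not supply balance or masking.

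The risk differs by comparison:

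- **Ultrasound correlation:** clearest risk, with inflation the likely direction; size not derivable.
- **Stiffness equivalence:** size unknown; under the assumptions in step 3 it matters only if the pull exceeds about 25%.
- **Success-rate non-inferiority:** neither size nor direction known.

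The primary analysis of FibroTouch against biopsy is not affected by this point. The change should be made because it is cheap and the analysis cannot supply it afterwards.

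**What to change.** 1. Require the ultrasound score to be entered and locked in the CRF before any stiffness measurement that day. Where a different person runs the stiffness devices, the score need not be passed on.
2. Set the order of FibroTouch and FibroScan from a pre-generated balanced list for each centre, record the order used, and include it as a term in the paired comparison. Parity of the IWRS subject number would not serve. Section VII issues that number only after the pathological stage is entered, while inclusion criterion 3 and item 5 allow biopsy after FibroTouch, so it may not exist at scanning. Item 7 describes biopsy only before FibroTouch, and these passages should be reconciled as well.
3. Where the two devices have different operators, do not pass on the first kPa until the second result is saved. Each operator still sees the reliability check on their own device, so the FibroTouch repeat rule is untouched. Where one person runs both devices, masking is not achieved and the balanced order is the main protection.
4. Reconcile the measurement-site wording in items 5, 6.1 and 6.2, and say whether site means centre or position on the body. If a common position is intended, it must be marked before the first device is used.

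Cost: minor scheduling effort and one extra CRF field, with no added visit or procedure.

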6.2 Operation procedure

(1) Keep in a supine position, lift up both hands to expose the intercostal gap in the area of right liver lobe of chest, and take a deep breath to make the intercostal gap as large as possible at the time of determination.

(2) Vertically stick the probe smeared with coupling agent to the intercostal gap.

(3) Determination site: Select the intercostal gap at the anterior or middle axillary line between the Rib 8~10 for routine determination, or adjust the determination site until the optimal one according to the real-time audiovisual diagram if the determination fails at the routine site.

(4) Observe the audiovisual diagram displayed in the instrument, and press the emission button for determination when there is a laminar liver image.

(5) Determine effectively for 10 times, and regard the mean of these 10 determinations as the determination result.

7. Liver biopsy

Within 3 months before the FibroTouch examination, puncture the 16G liver biopsy needle into 1.5~2.0cm of liver tissues (≥ 8 complete portal areas), fix with 10% neutral formalin, embed with paraffin wax, make the continuous section for HE, Masson and reticular fiber staining (make the HE staining at every study unit, and send another 6 white films to the central laboratory). Then, three pathologists interpret the films independently according to the standard and modified Chevallier semi-quantitative scoring method in the “Protocol for Prevention and Treatment of Viral Hepatitis (2001)”. The interpretation result of these three pathologists should be verified as well consistent through the Kappa test, and otherwise the specimen of inconsistent interpretation result is sent for central interpretation and evaluation.

(1) The liver fibrosis is staged and scored through the following protocol:

① National Protocol for Prevention and Treatment of Viral Hepatitis (2000): staging of liver fibrosis

② Chevallier System (SSS scoring)

③ Metavir System

④ Ishak System

(2) Evaluation protocol for inflammatory activity level and histological activity index (HAI):

① National Protocol for Prevention and Treatment of Viral Hepatitis (2000): grading of inflammation severity

② Ishak Modified HAI: ____/18 (maximum score)

③ METAVIR System: histological activity score

(IV) Safety Evaluation

1. Clinical Safety Evaluation

The clinical safety is evaluated through the adverse events reported by the patients or observed by the doctors.

2. AE

Definition: Any adverse medical event reported by the patients or observed by the doctors from the signing of ICF and recruitment into study to the final follow-up, either at a causality correlation with the study device or not.

(1) AE record

During the study, the occurrence time of AE, its correlation with study device, its severity, duration, countermeasures and prognosis should be recorded strictly by the facts.

The AEs should be recorded into the assigned CRF of adverse events.

(2) Judgment criteria for AE severity

◆ While filling in the CRF, the investigators will describe the intensity of AE in the following grading criteria:

Mild: No influence on the normal function of subjects;

Moderate: A certain influence on the normal function of subjects;

Serious: Obvious influence on the normal function of subjects.

(3) Judgment criteria for correlation between AE and study device

The investigators should evaluate the possible correlation between AE and study device in the following principles:

- ① Whether there is a rational precedence relation between the starting time of FibroTouch examination and the occurrence time of AE;
- ② Whether the suspicious AE conforms to the known type of AE for this device;
- ③ Whether the suspicious AE can be interpreted by the clinical state of patients or the influence of other therapies;
- ④ Whether the AE disappears or is relieved after the suspension of examination.

According to the above principles, the correlation is classified into 5 grades: definitely relevant, probably relevant, possibly relevant, possibly irrelevant and irrelevant.

(4) SAE:

◆ Judgment of SAE: Under one or more following conditions, the AE is regarded as a SAE: ① Death; ② Life-jeopardizing (e.g. risk of immediate death); ③ Induced or prolonged hospitalization; ④ Influenced working ability; ⑤ Permanent or serious

disability; ⑥ Congenital malformation or defect. If a certain medical event of no death, life-jeopardization or hospitalization may harm the patient or require the medicines or surgery to prevent the occurrence of above conditions in the viewpoint of study doctor, such event should also be regarded as SAE.

◆ Treatment of SAE: If the AE is irrelevant to study device and does not seriously influence the patient and the patient can be followed up as scheduled, the study should be continued. Under the other conditions, the patient should drop out.

◆ Recording and reporting of SAE: Any SAE during this study should immediately be reported to the supervisor, sponsor and national medicine clinical study institution (i.e. leading unit), which should report to the Ethic Committee and then within 24h to the CFDA and health administrative departure Meanwhile, the investigators must fill in the “Reporting Form of Serious Adverse Events”, and record the occurrence time, severity, duration, countermeasures and prognosis of SAE. If a patient suddenly dies during the study, such event should be reported as SAE, and the autopsy report should be enclosed if any.

(V) Quality Control and Quality Assurance of Clinical Study

◆ The participants must pass the uniform training on the uniform recording method and judgment criteria.

◆ The investigators must work strictly according to this protocol, fill in all study materials in an accurate timely complete neat way, so as to ensure the true reliable contents of report.

◆ Any observation result and finding during this study should be verified so as to ensure the reliability of data and guarantee that every conclusion of clinical study stems from raw data. At the stage of clinical study and data processing, there should be corresponding measures for data management.

◆ During this study, the clinical supervisor will regularly or irregularly make the field supervisory visit to the study center. According to the relevant regulations, the supervisor has the right to check the original record and remind/urge the investigators to carefully normatively complete the study work; and the investigators are liable to coordinate with such work.

(VI) Ethical Requirements and Informed Consent

◆ No subject can be enrolled in the study before he or she express his/her willingness to participate in this study in written statement. To make this decision, subjects should be informed of content of this study and the potential risks and benefits involved.

The investigator must inform this information in both spoken and written form. Informed consent should be obtained from the participants (or legally authorized representative or Witness, if applicable) prior to any other study assessment. A copy of the signed Informed consent form (ICF) will be given to patients.

After signed ICF, the subject's investigational data can be collected. The information in ICF involved in clinical study may be released and monitored by the Sponsor, device regulatory authorities, designated auditors and monitors according to the confidentiality statement.

◆ The following information should be told to the patient: objective and procedure of study; benefits and possible side effects for participation into the clinical study; the privacy of each patient should be protected; and at any study-related injury during this study, the investigators will give the active treatment and the sponsor will make the proper compensation.

◆ Before the initiation of this study, the permission of Ethic Committee should be obtained, and the written certificate for such permission should also be obtained. According to the guideline of GCP, this protocol can be modified only after the permission of Ethic Committee. If such modification may endanger the patient, the contents of ICF should be updated, and the signed consent should be obtained from the participating patients. This study should observe the Helsinki's Declaration and national specifications/regulations on clinical study, and can be made only after the permission of relevant institutions.

(VII) Statistical Analysis of Data

After the determination of study protocol, the statisticians should discuss with the principal investigator on preparing the statistical analytical plan. The data is analyzed through the statistical software SAS 9.3 (authorization No.: 11202165). The sample size is calculated through the software PASS 11. The contents of statistical analysis are classified into the

following parts:

1. Basic description: Age, sex, medical history and relevant indices of laboratory examination (e.g. ALT and AST). For the quantitative indices, the mean, standard deviation, median, minimum value, maximum value, lower quartile (Q1) and upper quartile (Q3) will be described; and for the classification indices, the case amount and percentage in each category will be described.

2. Evaluation of diagnostic ability via elasticity determination result

◆ By grouping according to the grading result via golden standard, the inter-group comparison is made on the FibroTouch determination results through the variance analysis or Wilcoxon rank-sum test, the correlation between two groups is tested through the Spearman correlation analysis, and the correlation coefficient (r) and 95% CI are calculated for two groups.

◆ By regarding the different grading results of golden standard as the judgment critical point, the curve of receiver operating characteristic (ROC) for elasticity value is constructed. The subjects are grouped by regarding the different determination results of elasticity value as the judgment critical point, the sensitivity/specificity is calculated according to the grading result of golden standard, the ROC curve is plotted through the X-axis of specificity, the Y-axis of sensitivity and the calculated result, and the area under curve and its 95% confidence interval are calculated. The critical value corresponding to whichever is greater for the result of sensitivity and specificity is regarded as the judgment critical point for FibroTouch determination value, and then the corresponding sensitivity, specificity, positive predicted value and negative predicted value are calculated.

Comparison of secondary objective: by statistically assuming the success rate of FibroTouch is non-inferior to that of Fibroscan, the critical value of non-inferiority is 10%; and by statistically assuming the determination result of FibroTouch is equivalent to that of Fibroscan, the critical value of equivalence is 1.5KPa.

In the above analysis, $P < 0.05$ indicates a significant difference.

(VIII) Data Management and Data Traceability

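### FibroScan is to share FibroTouch's measurement site, but the two procedures name different routine positions and breathing, which can enter the 1.5 kPa equivalence comparison as a device difference

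*Combined protocol and SAP*

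**What the plan says.** Section IX (III) 6.1 sets the link between the two examinations: "At the same site as that for FibroTouch, the stiffness of liver is determined via Fibroscan at the same day".

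The procedures themselves read as follows.

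- **FibroTouch position** (IX (III) 5, step 2): gel and the B-mode probe go on the right side at the "interspace between the Seventh and eighth rib along the midaxillary line". The operator then has latitude: "Investigator can choose the proper position for liver examination with reference to the ultrasonic B image on the video display screen". The rules for the final testing point concern the tissue (away from vessels, cysts, nodes and the liver edge; homogeneous; at least 7 cm thick) and name no rib.
- **FibroTouch breathing** (step 4): "With subject holding his or her breath slightly, operator observes the liver tissue displayed by ultrasonic-M signal".
- **FibroScan position** (6.2 item 3): "Select the intercostal gap at the anterior or middle axillary line between the Rib 8~10 for routine determination". The operator may adjust the position, but only "if the determination fails at the routine site".
- **FibroScan breathing** (6.2 item 1): the patient is to "take a deep breath to make the intercostal gap as large as possible at the time of determination".
- **Summary of readings**: for FibroTouch, "Each subject will obtain 10 successful acquisitions and the median value of these acquisitions will be considered as the examination result". For FibroScan, 6.2 item 5 takes the mean of the 10.

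The difference between the devices in measured values is a secondary objective (II (II)). Section IX (VII) tests it as equivalence with a 1.5 kPa limit, and tests the success rate as non-inferiority with a 10% limit. The analysis text plans no adjustment for position or breathing.

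**The concern.** An equivalence test on paired readings is meant to isolate the device. Here position and breathing can vary systematically with device within each patient. The mean paired difference then estimates the device effect plus any effect of position and breathing, and the design gives no way to separate them. A larger sample does not help, because this is bias and not noise. Depending on its direction, the bias can hide true equivalence or produce an apparent one.

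There is also a practical conflict. If *site* in 6.1 means body position, an operator who starts FibroScan at the routine position of 6.2 does not meet 6.1. Centres could resolve that differently, so the comparison might not mean the same thing across centres.

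**Working it through.** **1. The procedures side by side**

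| | FibroTouch (IX (III) 5) | FibroScan (6.2) |
|---|---|---|
| Named space | ribs 7–8 | ribs 8 to 10, that is 8–9 or 9–10 |
| Axillary line | middle | anterior or middle |
| Breathing | slight hold | deep breath |
| When position may change | chosen on the B-mode image | only if the routine site fails |
| Summary of 10 readings | median | mean |

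The named spaces share rib 8 as a border but have no space in common. The mid-axillary line is open to both devices. Because the FibroTouch point is finally chosen on the image, the positions actually used may coincide in some patients.

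**2. What *site* means in 6.1**

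The bullet just before 6.1 uses the word for a study centre. Item 3 of 6.2, within the same FibroScan section, uses it twice for body position. The second use is closer in subject, so the anatomical reading is the more natural one. On that reading 6.1 and 6.2 item 3 conflict. On the centre reading there is no conflict, but the protocol then itself sends the two devices to different routine positions. Position can vary with device on either reading.

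**3. How much a shift would matter**

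The plan states no sample size, power or paired SD for the equivalence test, so it has no figure of its own to reproduce. The documents also give no position or breathing effect. What follows shows sensitivity only.

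Inputs from the documents: margin m = 1.5 kPa (IX (VII)); n = 500 final cases (V); level 0.05 (IX (VII), sidedness not stated).

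Assumptions: two one-sided tests at 0.05 each; a valid reading on both devices for all 500; paired SD s of 3, 5, 8 or 10 kPa; net mean shift b of 0, 0.5 or 1.0 kPa.

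With SE = s/√500, the probability of declaring equivalence is

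Φ((m − b)/SE − 1.645) − Φ((−m − b)/SE + 1.645).

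Example with s = 5 and b = 1.0: SE = 5/22.36 = 0.2236. Then (1.5 − 1.0)/0.2236 − 1.645 = 0.591 and Φ(0.591) = 0.723. The second term is negligible.

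| Net shift b | s = 3 | s = 5 | s = 8 | s = 10 |
|---|---|---|---|---|
| 0 | 1.000 | 1.000 | 0.989 | 0.913 |
| 0.5 kPa | 1.000 | 0.998 | 0.875 | 0.720 |
| 1.0 kPa | 0.981 | 0.723 | 0.402 | 0.299 |

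- *Masking equivalence.* For identical devices, the rows give the power left after a pure position shift of b.
- *Creating equivalence.* Suppose the devices truly differ by 1.5 kPa, where the error rate should be 0.05, and a 0.5 kPa shift acts the opposite way. The net difference is 1.5 − 0.5 = 1.0 kPa, so the last row applies: equivalence is declared with probability 0.981, 0.723, 0.402 or 0.299.

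A 0.5 kPa shift would use 0.5/1.5 = 33% of the margin, and 1.0 kPa would use 67%.

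**The case against.** - **The wording may not conflict at all.** If *site* means centre, 6.1 asks only for the same centre on the same day. That reading is possible and cannot be excluded. It removes the contradiction but not the difference in routine position and breathing.
- **The probe can move.** A reader might infer from the named spaces that the devices never measure the same place. The documents do not support that, because both procedures allow movement. What stands is that the latitude is unequal and nothing in 6.2 tells the FibroScan operator to match the FibroTouch point. Step 3 saves the B-mode image for FibroTouch; 6.2 has no matching instruction to record the space used. The CRF is not in the documents, so it may already capture this.
- **Each device by its own procedure is a legitimate comparison.** This is correct. Position is then part of the measuring system and not a bias. But the plan does not declare that comparison, and the same-site wording points the other way.
- **The size is unknown.** This stands in full. A reader might also set the 1.5 kPa limit against the 1.1 kPa gap (6.6 − 5.5) between the F0-1 and F2 medians in the background. That is a between-stage gap in a hepatitis C cohort and says nothing about position.
- **Aligning position alone would not isolate the device.** This is also true. The median-versus-mean difference is unambiguous and belongs in the same correction. The 0.3 limit on the IQR-to-median ratio is likewise stated only for FibroTouch.

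**Conclusion.** The point holds as a should-fix matter for a secondary objective. The routine positions and breathing instructions differ by device, matching is not secured, and 6.1 most naturally says that the positions should match. Together with the different summary statistics, this means the 1.5 kPa result cannot be read as a pure device effect. The success-rate comparison may also be affected.

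The bias cannot be sized or signed from the documents. Under the assumptions above, a 0.5 kPa shift is almost harmless at a paired SD of 3 or 5 kPa, while a 1.0 kPa shift is serious at 5 kPa or more. Neither the shifts nor the SDs come from the plan. A reader might infer that the equivalence result is bound to be wrong, or that diagnostic accuracy is compromised. Neither is supported: no effect of position or breathing is shown, and the primary comparison of FibroTouch with biopsy does not use FibroScan readings.

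**What to change.** Reconcile the FibroTouch steps in IX (III) 5 with 6.1 and 6.2. The sponsor chooses the rule; this review does not say which position or breathing instruction is right. There are two coherent options:

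1. State one position and one breathing state for both devices, and say how FibroScan is to be placed at the point chosen for FibroTouch.
2. Remove the same-site wording from 6.1, record the interspace and axillary line used for each device, and limit the equivalence conclusion in IX (VII) to each device used by its own procedure.

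If *site* in 6.1 was meant as centre, say so and follow option 2.

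In the same edit, name one summary statistic of the 10 readings for both devices in the equivalence analysis.

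The cost is procedure wording and a small CRF addition. No extra examination is needed.
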